Randomized Open-Label Trial to Compare the Immunogenicity of Cell Culture-Based and Recombinant
Unadjuvanted Quadrivalent Influenza Vaccines to Conventional Egg-Based Unadjuvanted Quadrivalent Influenza
Vaccines among Healthcare Personnel Aged 18-64 Years:

Year 2 Protocol Amendment

NCT03722589

Document Date: July 11, 2019

1. Protocol Title

Randomized Open-Label Trial to Compare the Immunogenicity of Cell Culture-Based and Recombinant Unadjuvanted Influenza Vaccines to Egg-Based Influenza Vaccines among Healthcare Personnel Aged 18-65 Years:

Year Two Amendment

Background

The first year of this randomized, open-label trial conducted during the 2018-2019 influenza season assessed humoral and cell-mediated immune responses to cell culture-based and recombinant unadjuvanted quadrivalent influenza vaccines compared to conventional egg-based unadjuvanted quadrivalent SD (SD) (15 μ g of HA per strain) influenza vaccines among healthcare personnel (HCP) aged 18-64 years at two sites in the United States. Eligible participants were randomized 2:2:1:1 to receive a single dose of cell culture-based vaccine (FlucelvaxTM Quadrivalent by Seqirus, Inc., 15 μ g of HA per strain) versus recombinant vaccine (Flublok[®] Quadrivalent by Sanofi Pasteur, 45 μ g of HA per strain) versus one of two egg-based SD vaccines (Fluzone[®] Quadrivalent by Sanofi Pasteur, 15 μ g of HA per strain and Fluarix[®] Quadrivalent by GlaxoSmithKlein, 15 μ g of HA per strain) during October 2018. The first year of the trial was designed to address the question of whether HCP who receive cell culture-based or recombinant influenza vaccines for the first time (after receipt of egg-based SD vaccines in previous seasons) have higher antibody titers (surrogates for immune protection^{1,2}) against circulating influenza viruses compared to HCP who receive egg-based SD vaccines.

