Compare immune responses after two consecutive years of vaccination with cell-based influenza vaccine (Flucelvax™ Quadrivalent) or recombinant influenza vaccine (Flublok® Quadrivalent) versus first time receipt of these vaccines following vaccination with SD egg-based influenza vaccines.	Flucelvax™ Quadrivalent year one/year two	SD egg-based vaccine year one/Flucelvax™ Quadrivalent year two
	Flublok® Quadrivalent year one/year two	SD egg-based vaccine year one/Flublok® Quadrivalent year two
Compare immune responses after two consecutive years of vaccination with cell-based influenza vaccine (Flucelvax™ Quadrivalent), recombinant influenza vaccine (Flublok® Quadrivalent), or SD egg-based vaccine (Fluzone SD).	Flucelvax™ Quadrivalent year one/year two	SD egg-based vaccine year one/year two
	Flublok® Quadrivalent year one/year two	SD egg-based vaccine year one/year two

Compare immune responses after cell culture-based influenza vaccine (Flucelvax™ Quadrivalent) versus recombinant influenza vaccine (Flublok® Quadrivalent) at approximately 28 days after receipt of the 2019-2020 vaccines, regardless of prior vaccination status.	Flucelvax™ Quadrivalent year 2 (regardless of year one vaccine)	Flublok® Quadrivalent year 2 (regardless of year one vaccine)
Compare immune responses after first time vaccination with cell-based influenza vaccine (Flucelvax™ Quadrivalent), recombinant influenza vaccine (Flublok® Quadrivalent), or high-dose egg-based vaccine (Fluzone High-Dose) following vaccination with SD egg-based influenza vaccines to repeated vaccination with SD egg-based vaccine.	SD egg-based vaccine year one/Flucelvax™ Quadrivalent year two SD egg-based vaccine year one/Flublok® Quadrivalent year two Fluzone HD year two	SD egg-based vaccine year one/year two

SD: Standard dose; HD: High dose

Power/Sample Size Calculations:

Study sample size was determined based on available resources. An overall sample size of up to 830 with

- 90 participants each in the Flublok® Quadrivalent year one/ Flucelvax™ Quadrivalent year two group and Flublok® Quadrivalent year one/year two group
- 135 participants each in the Flucelvax™ Quadrivalent year one/year two group and Flucelvax™ Quadrivalent year one/ Flublok® Quadrivalent year two group
- 100 participants each in the SD (SD) egg-based vaccine year one/Flucelvax™ Quadrivalent year two, SD egg-based vaccine year one/Flublok® Quadrivalent year two, and SD egg-based vaccine year one/year two groups, and

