- 80 participants in the Fluzone HD year two group

would provide adequate statistical power to detect a post-vaccination GMT ratio of 1.2 between comparison groups as outlined in table 5 after adjusting for up to seven comparisons using a Bonferroni correction. Table 6 provides estimated sample sizes per comparison group required for varying post-vaccination GMT ratios after adjustment for up to eight comparisons.

Table 6. Sample size calculations to detect specified post-vaccination GMT ratios between two comparison groups after adjustment for eight primary comparisons using a Bonferroni correction

GMT ratio	N per group
1.5	16

1.4	22
1.3	34
1.2	69
1.1	245

Vaccine Product:

Four vaccine products will be used during the 2019-2020 season of this trial: Fluzone® Quadrivalent, Flucelvax™ Quadrivalent, Flublok® Quadrivalent, and Fluzone Trivalent High Dose. CDC or study sites will purchase vaccine. Fluzone® Quadrivalent, Flucelvax™ Quadrivalent, and Flublok® Quadrivalent are inactivated influenza vaccines that are approved for use in adults aged ≥ 18 years in the United States. Fluzone Trivalent High Dose is an inactivated vaccine that is licensed for use in adults aged ≥ 65 years in the United States and will be used off-label in this trial. All four vaccine products will contain vaccine strains representative of the following three strains in the 2019-2020 formulation: an A/Brisbane/02/2018 (H1N1)pdm09-like virus; A/Kansas/14/2017 (H3N2)-like virus; and a B/Colorado/06/2017-like virus (B/Victoria/2/87 lineage). All quadrivalent vaccine products will also include a B/Phuket/3073/2013-like virus (B/Yamagata/16/88 lineage).

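### Planned year-two groups imply 270 former Flucelvax to 180 former Flublok recipients, unexplained under 2:2:1:1; reconcile the counts and put site and age group in the Objective 1 and 3 models

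*Combined protocol and SAP*

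**What the plan says.** The Background section describes year one as follows: "Eligible participants were randomized 2:2:1:1 to receive a single dose of cell culture-based vaccine", with the other shares going to Flublok (2) and to two egg-based vaccines (1 each). Flucelvax and Flublok should therefore be equal in number, and the two egg-based arms together should equal either of them.

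Power/Sample Size Calculations then lists the year-two groups:

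- Former Flublok: "90 participants each in the Flublok® Quadrivalent year one/ Flucelvax™ Quadrivalent year two group and Flublok® Quadrivalent year one/year two group".
- Former Flucelvax: "135 participants each in the Flucelvax™ Quadrivalent year one/year two group", and the same number in the group switching to Flublok.
- Egg history: "100 participants each in the SD (SD) egg-based vaccine year one/Flucelvax™ Quadrivalent year two", with two further egg-history groups of the same size.
- High dose: "80 participants in the Fluzone HD year two group".

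The section introduces these groups with "An overall sample size of up to 830 with" and gives the basis as "Study sample size was determined based on available resources".

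Under Study Design, all year-one participants must consent again. Former Flucelvax and former Flublok recipients are re-randomised 1:1 to those two vaccines. The egg-history pool is randomised 1:1:1 and may be topped up at each site to 150. The section on year-two randomisation treats new main-trial enrollees as egg-history participants and stratifies by age group within site.

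Statistical Analysis for Year Two names a repeated-measures mixed model with time point, vaccine and their interaction. It allows ANOVA adjustment where arms turn out unbalanced, without naming a covariate. Seroconversion may be compared by chi-square tests.

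**The concern.** Each former-vaccine pool is split 1:1 in year two, so doubling the group size recovers the number expected from that year-one arm. The result is 3:2 for two arms described as equal. New enrollees join only the egg-history groups or the high-dose arm, so they cannot produce the difference.

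This matters because of what Objectives 1 and 3 compare. Table 5 gives four contrasts: Flucelvax in both years against egg/Flucelvax and against egg/egg, and Flublok in both years against egg/Flublok and against egg/egg. Each sets one vaccine-history pool against another. Year-two randomisation works within pools, so it does not make these groups comparable. Comparability rests on year-one allocation, on who comes back, and on the egg-history top-up. If any of these differs by site or age, the contrast mixes vaccine history with site or age unless the model accounts for it.

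**Working it through.** **1. Reproduce the plan's total.** 2 x 90 + 2 x 135 + 3 x 100 + 80 = 180 + 270 + 300 + 80 = 830. This matches, so the group sizes have been read correctly.

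**2. Implied year-one sources.** Former Flucelvax 270, former Flublok 180; 270/180 = 1.5. Equal arms with equal return would split the same 450 as 225:225, or 112.5 per year-two group instead of 135 and 90.

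**3. What could produce 3:2.**

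- *Return:* with equal year-one arms, Flublok recipients return at two thirds of the Flucelvax rate, for example 60% against 90%, or 53% against 80%.
- *Allocation:* a fraction f of the 450 was allocated where or when Flublok was not given. Then f + (1 - f)/2 = 0.6, so f = 0.2, or 90 people.
- *Resources:* the targets were simply set unequally.

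The document gives no year-one counts or return figures, so it cannot separate these.

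**4. Power.** Table 6 states neither SD nor power. Assuming 80% power and two-sided alpha 0.05/8, its entry of 69 per group at a ratio of 1.2 implies a ln-titre SD of ln(1.2) x sqrt(69/2) / (2.734 + 0.842) = 0.30. At that SD, power against an egg-history group of 100 is about 93% with 90 participants, 97% with 135, and 95 to 96% with 112.5. The imbalance does not endanger the stated power.

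**5. Objective 2.** Flucelvax in year two: 135 + 90 + 100 = 325. Flublok in year two: 135 + 90 + 100 = 325. Each pool contributes equally to both sides by randomisation, so unequal pool sizes do not bias this contrast.

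**6. Objectives 1 and 3: illustration of site mix.** The egg-history pool is aimed at 150 + 150 = 300, so 50:50 by site. The site mix of the other pools is not given, and every site split and site difference below is an assumption. If shares s1 and s2 of the two compared groups come from one site, and GMT at that site is g times that at the other, the unadjusted GMT ratio is multiplied by g^(s1 - s2).

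- *Whole Flublok shortfall at one site:* Flucelvax 135:135, Flublok 135:45, so s1 = 0.75 for Flublok. With g = 1.25, 1.5 and 2, g^0.25 = 1.06, 1.11 and 1.19. The Flucelvax contrasts are unaffected.
- *Equal totals per site (225 each):* Flucelvax:Flublok is 112.5:112.5 at one site and 157.5:67.5 at the other. The first site's share is 112.5/180 = 0.625 for Flublok and 112.5/270 = 0.417 for Flucelvax. With g = 1.5 the factors are 1.5^0.125 = 1.05 for Flublok and 1.5^(-0.083) = 0.97 for Flucelvax. Here all four contrasts move.
- *Wider range:* shares of 60% to 90% and g from 1.2 to 2.0 give 1.2^0.1 = 1.02 up to 2^0.4 = 1.32.

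**7. Composition of the egg-history pool.** Under 2:2:1:1 the egg-based arms together equal each other arm. If their recipients return as Flucelvax recipients are planned to (270), 300 - 270 = 30 of the pool are new (10%). If they return as Flublok recipients are planned to (180), 300 - 180 = 120 are new (40%). New enrollees were never randomised in year one, and the document does not say how many are expected.

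**The case against.** The figures are rounded ceilings for year two, set by resources and applying after renewed consent. The Background statement reports how people were randomised. Both can be true, so neither need be an error. No figure links the shortfall to site, and an unequal ratio does not by itself bias a contrast. The smallest group, 90, exceeds the 69 in Table 6. The analysis section allows adjustment for imbalance, randomisation is stratified by site and age, and methods not changed by the amendment carry over from the original protocol, which is not available here. Figure 3, with per-site goals, is not shown either.

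Most of this stands. A reader might infer from 270:180 that year-one randomisation was not carried out as described. The document does not support that, because lower return among Flublok recipients gives the same numbers. A reader might also test 270:180 against 1:1 with a binomial test. Planning targets are not sampled counts, so a p-value would have no meaning.

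Two parts do not answer the point. Resources are a weak explanation on their own: no arm-specific limit on re-enrolment appears, and a limit would have to fall on former Flublok recipients alone. A general permission to adjust, with no covariates named, does not ensure that the factors used in randomisation enter the model.

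**Conclusion.** The concern holds in a limited form. The 270:180 split is unexplained under 2:2:1:1 and needs reconciling. Its cause cannot be determined from the document. It leaves the stated power and Objective 2 intact.

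The analytic consequence is that the four Objective 1 and 3 contrasts compare pools filled by different mechanisms, under a named model without site or age group. The resulting bias cannot be estimated from the document. The factors of 1.02 to 1.32 show only that assumed site mixes and site differences could produce shifts comparable with the target ratio of 1.2.

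It is tempting to conclude that the shortfall sits at one site and that a site term cures it. Nothing shows the first. The second fails if the cause is selective return within site, which a site term would not remove. The case for site and age group rests on firmer ground: they are the existing randomisation strata, and the compared pools are not balanced on them by design.

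**What to change.** 1. **Model.** Include site and age group (18-44, 45-65) as terms in the four Objective 1 and 3 contrasts for GMT and MFR. For seroconversion, replace the plain chi-square test in these contrasts with a comparison stratified by the same factors. The cost is two model terms, both already recorded for randomisation.
2. **Counts.** Add a short table of year-one numbers randomised and expected to return, by arm and site, and the number of new enrollees expected in the egg-history pool. Use it to explain 270:180 against 2:2:1:1, or to correct whichever statement is wrong.
3. **Conditional step.** Only if those counts show that Flublok was not allocated at a site or in a period, limit the Flublok-history contrasts to participants randomised in year one while all arms were open. This would remove some egg-history participants, including new enrollees, from those contrasts.

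Weighting by the probability of return is not recommended: it cannot be computed for new enrollees, who were never in year one.
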